5.3 Patient Withdrawal Criteria

All patients are free to discontinue study treatment or withdraw from the study at any time. All patients wishing to discontinue from study treatment or withdraw from the study will be queried to determine the reason for withdrawal while respecting the privacy of the patient. The reason a patient decided to withdraw from study treatment will be recorded.

Confidential and Proprietary

In the event of consent withdrawal, the Investigator should make every effort to ensure that the patient is followed for AEs for a minimum of 30 days after their last dose of study treatment, with documented patient agreement.

Patients will be discontinued from study treatment if any of the following events occurs:

- Any unacceptable toxicity attributable to study treatment (e.g., hepatotoxicity meeting Hy's Law criteria)
- Progressive disease according to RECIST v1.1 at any time during the study
 - o Unless approved by the Medical Monitor (See Section 6.6)
- Clinical progression (e.g., symptomatic deterioration) not meeting the RECIST v1.1 criterion for progressive disease but considered by the Investigator to require withdrawal from study treatment
- Patient is unable to tolerate dosing after more than 2 dose reductions
- Patient misses 2 doses
 - Exception: Patients who miss 2 doses may continue study treatment following agreement between the Investigator and the Medical Monitor.
- Significant deviation from the protocol or eligibility criteria. These patients may continue study treatment following a discussion and agreement between the Investigator and the Medical Monitor and subsequent approval by the institutional review board (IRB) or independent ethics committee (IEC).
- Pregnancy
- Patient withdrawal of consent and/or election to discontinue study treatment
- Termination of the study by the Sponsor
- Any other reason which, in the opinion of the Investigator, would justify removing the patient from the study treatment

A patient may also be withdrawn from study treatment by the Sponsor, Regulatory Authorities, or IECs/IRBs.

If a patient discontinues study treatment due to the ongoing coronavirus disease 2019 (COVID-19) global pandemic, information should be captured on the eCRF so that this can be summarized in the clinical study report at the end of the study, in line with the FDA Guidance (FDA 2020). The reason for discontinuation should be recorded in the eCRF as COVID-19, if applicable, and include as many details as possible. For example, specific reasons may include, but are not limited to:

- The patient exhibits symptoms consistent with COVID-19.
- The patient has a positive test result for COVID-19.
- The patient has neither symptoms nor a positive test for COVID-19 but has decided to discontinue treatment due to personal choice related to COVID-19 concerns.

Confidential and Proprietary

Patients who are discontinued from study treatment for reasons other than progressive disease by RECIST v1.1 should undergo scans for tumor assessment according to the original tumor assessment schedule (every 8 weeks [± 5 days] from Cycle 1 Day 1) until any of the following occurs, whichever comes first:

- Progressive disease (PD) by RECIST v1.1,
- Initiation of new anticancer treatment, or
- Discontinuation from the study (death, withdrawal of consent, or loss to follow-up).

After discontinuation from study treatment, all patients will have an End-of-Treatment Visit (EOT). All patients, including those discontinued due to PD, will undergo a post-treatment Safety Follow-up Visit at 30 days (± 7 days) after last tarloxotinib infusion.

[figure not shown]
Withdrawal from the study should be in a step-wise fashion. As mentioned above, patients may withdraw or be withdrawn from study treatment. Any patient who withdraws or is withdrawn from study treatment should be encouraged to complete all planned safety and follow-up assessments. If the patient wished to withdraw from all study assessments, permission should be requested to contact the patient, a designated contact person, or the patient's primary care provider. If the patient does not wish any direct follow-up, permission should be requested to conduct periodic medical record review and/or contact the patient's medical care provider.

6. TREATMENT OF PATIENTS

6.1 Patient Enrollment

Prior to any study-related assessments, all potential patients will provide written informed consent. Informed consent can be obtained any time prior to Cycle 1 Day 1. All patients who provide informed consent will be assigned a unique patient identification number consisting of 6 digits, the first 3 digits will represent investigational site and the second 3 digits will identify the patient within that site (Figure 13); patient numbering within sites will begin with the number "– 201." Once a patient identification number has been assigned, it will be used to identify the patient throughout the study and it cannot be reassigned to another patient.

Figure 13: Sample Patient Identification Number

All potential patients must be approved by the Medical Monitor prior to enrollment. Investigational sites will provide the Medical Monitor with a completed Eligibility Checklist and relevant redacted source documents. The Medical Monitor (or designee) will review the provided documentation and confirm the patient's preliminary eligibility. The Medical Monitor

Confidential and Proprietary

(or designee) should be able to respond within 1 business day. Following review of the provided documentation, the Medical Monitor (or designee) will notify the investigational site if the patient appears eligible. Patients who meet eligibility criteria may be enrolled. Patients will be considered enrolled after receiving any tarloxotinib.

6.2 Tarloxotinib Administration

Tarloxotinib will be administered as an IV infusion using an IV infusion or syringe pump and a 0.2-micron inline filter. Tarloxotinib may be infused with latex-free polyvinyl chloride or polyolefin containers and equipment.

6.2.1 Tarloxotinib Dose Calculation

Tarloxotinib will be administered at a dose level of 150 mg/m². The dose administered will be based on the patient's body surface area (BSA) determined on Day 1 of each cycle or within 7 days (e.g., Day 21 of the prior cycle). The DuBois and DuBois formula for BSA calculation is:

BSA =
$$(W^{0.425} \times H^{0.725}) \times 0.007184$$

Investigational sites are instructed to use the DuBois and DuBois formula but may also use the formula/method in current institutional practice if accurate dose calculation can be assured.

Tarloxotinib doses within a cycle do not need to be adjusted unless there is a > 10% change in weight.

6.2.2 Tarloxotinib Infusion Duration

Tarloxotinib infusions must be at least 1 hour (60 minutes) in duration. The tarloxotinib infusion can be slowed or interrupted in the event of infusion-related reactions. If the tarloxotinib infusion is interrupted, it should be restarted at one-half the infusion rate after the symptoms of the infusion-related reaction have resolved.

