2.3.2 Clinical Trials

Study PR610-1001

A first-in-human Phase 1 clinical trial (Study PR610-1001) evaluated tarloxotinib administered as either a 1-hour or a 24-hour weekly intravenous (IV) infusion. The study was designed to determine the MTD and dose-limiting toxicities (DLTs) of tarloxotinib in patients with locally advanced or metastatic solid tumors. Twenty-seven patients received tarloxotinib administered weekly as a 1-hour infusion at doses ranging from 10 mg/m² to 200 mg/m² and 6 patients received tarloxotinib administered weekly as a 24-hour infusion at doses of 200 mg/m² or 335 mg/m². Of the patients who received tarloxotinib administered as a weekly 1-hour infusion, 6 patients received tarloxotinib at the recommended Phase 2 dose of 150 mg/m² tarloxotinib.

Confidential and Proprietary

DLTs with the 1-hour infusion included Grade 3 infusion-related reaction (150 mg/m²), Grade 3 facial pain (200 mg/m²), and Grade 4 QTc prolongation (200 mg/m²). An MTD of 150 mg/m² was declared for the 1-hour infusion duration. Other treatment-related AEs observed in the Phase 1 study included perioral paresthesia, musculoskeletal pain, nausea and vomiting, and dose dependent signs and symptoms of EGFR inhibition, notably skin rash, and diarrhea.

After the DLTs of Grade 3 facial pain (1) and Grade 4 QTc prolongation (1) were observed at 200 mg/m² administered as a 1-hour infusion, a 24-hour infusion duration was evaluated to determine if a reduced maximum peak plasma concentration (C_{max}) would reduce toxicities and allow higher weekly dosing. Three patients each were treated with a 24-hour infusion of tarloxotinib at 200 mg/m² or 335 mg/m². Treatment-related AEs were similar to those observed with the 1-hour infusion including nausea and diarrhea, skin rash and QT prolongation. A DLT of Grade 3 QTc prolongation was reported in 1 patient at 335 mg/m² at the 24-hour infusion duration.

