6.5 Treatment and Retreatment Criteria

The result of tumor assessments is not required for the initiation of subsequent cycles, but patients must meet the following criteria before receiving each tarloxotinib infusion. **Note:** all ECG dose modifications will be based on the average manually measured QTcF.

• No QTcF of \geq 601 msec during any previous infusion

Note: Patients with QTcF of ≥ 501 msec and < 601 msec during or following the prior infusion MUST be dose reduced. If QTcF prolongation is \geq Grade 3, an ECG may need to be repeated more frequently during a patient's visit as indicated in Table 7, depending on the degree of the prolongation and per institutional standards.

- Check serum electrolytes
 - Pre-infusion magnesium and calcium in normal range, unless an exception is approved by the Medical Monitor.
 - o If other electrolytes (eg, sodium, chloride) are outside of the normal range, patient can receive tarloxotinib infusion if it is deemed safe per Investigator discretion.
 - o Pre-infusion serum potassium must be ≥ 3.5 mEq/L.
- Pre-infusion ECG

Confidential and Proprietary

- o No evidence of second- or third-degree atrioventricular block
- o QTcF interval of < 450 msec
- Skin rash of \leq Grade 2
- Gastrointestinal toxicity of \leq Grade 2
- Any other clinically significant tarloxotinib-related toxicity must return to at least Grade 2.

All patients not meeting retreatment criteria must be discussed with the Medical Monitor (or designee) and possible dose/schedule modification and/or study treatment discontinuation discussed.

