6.7.2 Treatment Guidelines for Infusion-related Reactions

Treatment and management of infusion-related reactions will be based on the severity and type of symptom(s) experienced. Treatment guidelines for infusion-related reactions are presented in Table 8.

Table 8: Treatment Guidelines for Infusion-Related Reactions

Grade (CTCAE v5.0)	Definition	Treatment Guideline
Grade 1	 Mild transient reaction Infusion interruption not indicated Intervention not indicated 	 Monitor for at least 2 hours after the end of the infusion Provide patient instructions and prophylactic medications at discharge as appropriate Consider adjusting premedication based on symptoms for subsequent infusions
Grade 2	 Therapy or infusion interruption indicated but responds promptly to symptomatic treatment Prophylactic medications indicated for ≤ 24 hours 	 Administration of medications (e.g., anti-histamines, steroids, NSAIDs and IV fluids), as appropriate Monitor for at least 2 hours after the end of the infusion Consider adjusting premedication based on symptoms for subsequent infusions
Grade 3	 Prolonged (e.g., not rapidly responsive to symptomatic medication and/or brief interruption of infusion) Recurrence of symptoms following initial improvement, hospitalization indicated for clinical sequelae 	 Administration of medications (e.g., anti-histamines, steroids, NSAIDs and IV fluids), as appropriate Hospitalization for medical care and observation Reduce tarloxotinib dose to 120 mg/m² for subsequent doses*, or consider slowing infusion rate, and/or adjusted premedication after discussion with the Medical Monitor If Grade 3 infusion reaction recurs after this initial dose reduction, then reduce the tarloxotinib dose to 75 mg/m² for subsequent doses*
Grade 4	Life-threatening consequences Urgent intervention indicated	Hospitalization for urgent medical treatment Discontinue tarloxotinib permanently

CTCAE = Common Terminology Criteria for Adverse Events; IV = intravenous; NSAID = nonsteroidal anti-inflammatory drug

^{*} Dose re-escalation may be permitted following discussion and approval by the Medical Monitor

Confidential and Proprietary

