6.7.3 Treatment Guidelines for Other Non-Hematologic Toxicity

Table 9 provides treatment guidelines for treating tarloxotinib non-hematologic toxicities other than QT prolongation and infusion-related reactions.

Table 9: Treatment Guidelines for Tarloxotinib-Related Non-Hematologic Toxicity

Toxicity (CTCAE v5.0)	Details	Hold Dose	Dose Levels After Recovery to ≤ Grade 2 or Baseline
Grade 2 Intolerable	Intolerable skin toxicity or diarrhea	Hold dose until resolution to Grade 0 or 1 or Grade 2 tolerable	If symptoms are intolerable, recurrent, or not controlled by supportive care, hold dose until symptoms improve and reduce to next lower dose level
Grade 2	ALT or AST > 3 x ULN	Hold dose until resolution to < Grade 2 or baseline	150 mg/m ² (no reduction)
	ALT or AST > 3 x ULN (Grade 2) AND a total bilirubin \geq 2 x ULN (patients without liver metastasis)**	Treatment to be discontinued	Not applicable
Grade 3	Except nausea and vomiting*	Hold dose until resolution to Grade 0 or 1 or Grade 2 tolerable	120 mg/m ² ; if recurs, then second reduction to 75 mg/m ²
Grade 4	Life-threatening conditions	Treatment to be discontinued	Not applicable
Grade 4	Except fatigue and non-life-threatening pulmonary embolism that are adequately treated	Hold dose until resolution to Grade 0 or 1	120 mg/m²; if recurs, then second reduction to 75 mg/m²

ALT = alanine aminotransferase; ASP = aspartate aminotransferase; CTCAE = Common Terminology Criteria for Adverse Events; ULN = upper limit of normal

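### The half-rate restart rule in Protocol 6.2.2 has no grade limit and no link to Table 8: a literal conflict at Grade 4, and same-session re-exposure left open at Grade 3

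*Protocol*

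**What the plan says.** Protocol 6.2.2 sets a minimum infusion time of 60 minutes and lets sites slow or interrupt the infusion for infusion-related reactions. After an interruption, "it should be restarted at one-half the infusion rate after the symptoms of the infusion-related reaction have resolved". No grade is named and Table 8 is not cited.

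Protocol 6.7.2 makes management depend on severity, through Table 8:

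- **Grade 2** is defined by "Therapy or infusion interruption indicated but responds promptly to symptomatic treatment".
- **Grade 3** covers prolonged reactions and "Recurrence of symptoms following initial improvement". The guideline gives medication as appropriate and "Hospitalization for medical care and observation". It then offers 120 mg/m² "for subsequent doses*, or consider slowing infusion rate, and/or adjusted premedication after discussion with the Medical Monitor".
- **Grade 4** calls for hospitalization and permanent discontinuation.

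**The concern.** The two sections give different kinds of instruction for the same event. Section 6.2.2 tells the site to resume once symptoms clear, whatever the grade. Table 8 grades the response, but at Grade 3 its dosing line concerns later doses and is silent on the infusion in progress. A site that follows 6.2.2 to the letter could re-expose a patient in the session that caused a Grade 3 reaction, before any discussion with the Medical Monitor.

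What is at stake is patient safety. In the Phase 1 trial (Protocol 2.3.2), "DLTs with the 1-hour infusion included Grade 3 infusion-related reaction" at 150 mg/m², the starting dose here. Protocol 2.6 and 6.3 describe flushing, urticarial rash, itching and low blood pressure during or just after infusion.

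**Working it through.** The plan gives no figure to reproduce on this point. The check sets the provisions side by side, then sizes the cost of the fix.

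**Does 6.2.2 fit Table 8, grade by grade?**

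- *Grade 1:* interruption is not called for, so the restart rule has little to do.
- *Grade 2:* it fits. The definition is a reaction that warrants interruption and settles promptly.
- *Grade 3:* the restart condition can be met once symptoms have cleared. Table 8 directs medication and hospitalization and sets out options for later doses. It does not say whether the current infusion is abandoned. The slower-rate option carries a Medical Monitor discussion; the half-rate restart in 6.2.2 carries none.
- *Grade 4:* Table 8 stops the drug for good. Section 6.2.2, read alone, would still restart it.

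**Does another section settle Grade 3?**

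- Section 6.5: "patients must meet the following criteria before receiving each tarloxotinib infusion". This governs starting an infusion, not resuming one.
- Section 6.7.3 and Table 9 cover toxicities "other than QT prolongation and infusion-related reactions", so they do not apply.
- Section 6.3 covers premedication, and 8.4 with Table 11 covers reporting and grading.
- Section 5.3 requires treatment to stop for unacceptable toxicity and allows the investigator to stop for other reasons. It does not address an interrupted infusion.
- SAP 6.2 adds nothing on restarting.

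**Can the situation arise from following 6.2.2?** Yes. A Grade 2 reaction is interrupted, clears and is restarted at half rate; symptoms then return. That recurrence can meet the Grade 3 definition. Once symptoms clear again, 6.2.2 literally calls for another restart.

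**What would the fix cost a patient?** Inputs: 150 mg/m² (6.2.1) over the 60-minute minimum (6.2.2), weekly dosing (6.2.3), first scan at 8 weeks (6.9.2). Assumptions: constant rate, no other missed or reduced dose. The stop times are illustrative; the documents give none.

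- Full rate = 150 / 60 = 2.5 mg/m² per minute; half rate = 1.25.
- Dose left after stopping at *t* minutes = 150 − 2.5*t*; time to finish at half rate = dose left / 1.25.
- Planned dose before the first scan = 8 × 150 = 1,200 mg/m².

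| Stopped at | Given (mg/m²) | Left (mg/m²) | Time to finish at half rate | Left / 1,200 |
|---|---|---|---|---|
| 10 min | 25 | 125 | 100 min | 10.4% |
| 30 min | 75 | 75 | 60 min | 6.3% |
| 50 min | 125 | 25 | 20 min | 2.1% |

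**How often?** Not estimable. Section 2.3.2 lists the Grade 3 reaction without a count, and neither 2.3.2 nor 2.6 reports a Grade 4 infusion reaction.

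**The case against.** The case for leaving the text alone is substantial.

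- *The restart is conditional.* Symptoms must have resolved. A reaction that still meets the prolonged form of Grade 3 does not satisfy that, and the patient is to be hospitalized. This stands and is the main reason the risk is small. It does not cover a reaction that has cleared, and hospitalization is patient care, not an instruction about the infusion.
- *Section 6.2.2 is a rate rule, and the specific table governs.* Sections 6.7 and 6.7.2 send sites to Table 8, and an interrupted infusion is naturally read as different from a discontinued one. This largely answers Grade 4, which is a wording conflict only. At Grade 3 the table has no rule on resuming, so there is nothing specific to override 6.2.2. Protocol 11.2 also requires the protocol to be followed exactly, and 6.8 lists infusion duration and dose modification as compliance items. A site should not have to depart from the text to take the safer course.
- *Other guidance may exist.* Section 2.6 refers sites to the Investigator's Brochure for managing risks. That document is not available here, so the gap is shown only for the protocol and SAP.
- *The study is over.* SAP section 4 records early discontinuation and database lock on 23 April 2021. The value now lies in any reuse of this text.

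A reader might also infer that finishing 150 mg/m² after a Grade 3 reaction exceeds a 120 mg/m² limit. The documents do not support that: Table 8 offers a slower rate or changed premedication as alternatives to the reduction, so no protocol limit is breached. Nor does the Phase 1 dose-limiting toxicity show that a restart caused harm; it shows only that a Grade 3 reaction occurred at this dose.

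**Conclusion.** The point holds as a drafting gap with a bounded safety consequence. At Grade 4 the wording of 6.2.2 conflicts with Table 8 if read literally, though most sites would follow the table. At Grade 3 the wording permits same-session re-exposure without the Medical Monitor discussion that Table 8 ties to the slower-rate option, and no section checked says whether the infusion is abandoned.

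It would go too far to say that Table 8 gives no direction for a current Grade 3 event, since it directs medication and hospitalization. It would also go too far to say that the protocol orders a restart in a patient who is still reacting.

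The conclusion rests on the protocol and SAP text alone and on reading the Grade 3 slower-rate option as part of the line on later doses, where it sits without naming an infusion. No endpoint, sample size or error rate changes. Severity is minor: a cheap patient-safety improvement.

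**What to change.** Replace the last sentence of 6.2.2 with text to this effect:

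> *After an interruption for a reaction of Grade 2 or lower, the infusion may be resumed at half the rate once symptoms have cleared. An infusion stopped for a Grade 3 reaction, including a recurrence after a restart that meets Grade 3, is not resumed that day unless agreed with the Medical Monitor. An infusion stopped for a Grade 4 reaction is not resumed. See Table 8.*

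This keeps the restart where Table 8 supports it, applies the Medical Monitor route at Grade 3 instead of an absolute bar, and removes the Grade 4 conflict.

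*Cost.* A few sentences, plus the approvals that Protocol 11.2 requires for an amendment. A patient with a Grade 3 reaction may lose the rest of one weekly dose, as sized in the table above. SAP 9.2.16.2 already counts an interrupted infusion as one, so the infusion count is unchanged; that patient's dose intensity under SAP 9.2.16.4 falls slightly. Visits and data collection stay as they are.

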6.2.3 Tarloxotinib Administration Schedule

Tarloxotinib will be administered on Day 1, Day 8, Day 15, and Day 22 of every 28-day cycle. All infusions after Cycle 1 Day 1 will be administered 7 days \pm 1 day after the prior infusion. Investigators are instructed to avoid dose schedule modifications whenever possible, especially within the first 3 cycles of study treatment. The reason for the dose schedule modification should be recorded in the eCRF.

Dose Delays

All dose schedule modifications of > 1 day must be discussed with the Medical Monitor (or designee). Intentional cycle delays of > 1 day (e.g., patient vacation, physician requested "drug holiday") must be approved by the Medical Monitor (or designee). Study visits will align with tarloxotinib infusion days. If a tarloxotinib dose must be delayed > 3 days, this will be considered a missed dose.

Confidential and Proprietary

Missed Doses

If a patient misses a dose due to hospitalization or any other reason, the next dose received will be referred to as the next scheduled dose (e.g., If a patient misses their Cycle 1 Day 22 infusion, the next dose will be administered at their Cycle 2 Day 1 visit.). If a patient must miss their Cycle 2 Day 1 dose, the assessments that were planned for this visit (e.g. PK assessments and ECGs) should be collected at the Cycle 2 Day 8 visit to ensure adequate data is collected for these endpoints. For other missed visits, any assessments that were part of the missed visit, but are not part of the next visit (i.e., no need to duplicate tests) should be collected, if possible, at the next visit. Radiographic tumor assessments should continue per the Study Schedule (i.e., every 8 weeks [± 5 days] from Cycle 1 Day 1) regardless of changes to the dosing schedule.

If there is an unavoidable delay of an infusion due to COVID-19, the Medical Monitor should be informed as soon as possible. The infusion should be rescheduled based on Investigator judgment, taking into consideration the patient's safety.

